## **Appendix 8. Programming Specification**

- 1) AGE calculated as follows
  - a) AGE (years) is calculated from the number of days between the date of birth (DOB) and Day 1 (first dose date) defined for both randomized phase analysis and all B/F/TAF analysis. For subjects randomized to DTG + F/TAF group, AGE (years) is calculated for both randomized phase analysis and all B/F/TAF analysis.
  - b) Use the SAS INTCK function to determine the number of "1st-of-month days" (eg, January 1st, February 1st, March 1st) between DOB and Day 1 (inclusive),
  - c) Divide the result in (b) by 12,
  - d) AGE = the integer of the result in (c),
  - e) If the DOB and Day 1 have the month in common and the birthday is later in the month than the date of Study Day 1, then subtract one from the AGE result above.

For subjects randomized and never dosed with study drug, age will be calculated from the date of randomization.

Age for laboratory test reference range will be based on the age at the sample collection date.

- 2) All screened subjects refer to all subjects who are screened (ie, with non-missing screening date) and have a screening number. For summaries the same subject is counted only once. DOB and other demographic information such as sex, race, ethnicity, country, and initials will be used to identify unique screened subjects.
- 3) Screen failure subjects are the subjects who were screened and answered "No" for any inclusion criteria or "Yes" for any exclusion criteria regardless of which version of protocol the subject was consent to.
- 4) Subjects in the randomized analysis set are defined as subjects randomized into the study. IXRSRAND is the source to determine whether the subject is randomized (ie, subject with non-missing RGMNDTN in the IXRSRAND dataset), and confirmed by the eCRF ENROLL dataset (ie, ENROLLYN = "Yes" in ENROLL dataset).
- 5) Randomized treatment (ie, TRT01P in ADSL) are derived from IXRSRAND, while actual treatment received (ie, TRT01A in ADSL) is assigned as the randomized treatment if subject took at least 1 dose of study drug and assigned as blank if subject never dosed.
- 6) In disposition table, the reasons for premature discontinuation are displayed in the order as they appear on the eCRF.

7) Body mass index (BMI) and Body Surface Area (BSA)

BMI and BSA will be calculated only at baseline as follows:

- BMI = (weight [kg]) / (height [meters])
- BSA  $(m^2)$  = SQRT( [Height(cm) × Weight(kg) ] / 3600 )

Baseline height and weight will be used for this calculation.

- 8) SAS codes for the treatment comparison for demographics and baseline characteristics tables.
  - a) CMH test for nominal variable (Y), the p-value from general association test should be used for nominal variable:

```
proc freq order=adsl;
   tables trtgrp * Y /cmh /*general association test*/
run;
```

b) CMH test for ordinal variable (Y), the p-value from row mean score test should be used for ordinal variable:

```
proc freq order=adsl;
   tables trtgrp * Y / cmh2 ; /*row mean score test*/
run;
```

c) Wilcoxon rank sum test for continuous variable (Y), the p-value from the normal approximation two-sided test should be used for continuous variable:

```
proc npar1way wilcoxon data=adsl;
   class trtgrp;
   var Y;
run:
```

9) Please note, "Not Permitted", "Unknown", or missing categories will be excluded percentage calculation and also excluded for p value generation for categorical data analysis (eg, CMH test or Fisher exact test). Except for Mode of infection (HIV Risk Factors), where "Unknown" will be included for percentage calculation, since a subject may fit more than 1 HIV risk factors, therefore percentage may add to more than 100% and no p-value will be generated.

Subjects with Race = "Not Permitted" will also be excluded to define Race subgroup (ie, black vs. nonblack) for efficacy subgroup analysis.

10) SAS code for treatment comparison for duration of exposure. The p-value from log rank test should be used.

```
proc lifetest data=ADSL method=km;
  time TRTDURD*ESDD(0); /*Derive ESDD from COMT01FL, where ESDD = 0
  indicates censored observation (ie, subjects completed study drug)*/
  Strata TRT01AN;
  label TRTDURD = "Duration of Exposure (Days)";
run;
```

## 11) Last Dose Date and Last Study Date

a) Last Dose Date (ie, TRTEDTC, TRTEDT, TR01EDT or TR01EDTC) in ADSL for randomized phase analysis and all B/F/TAF analysis was defined in SAP Section 3.8.1.

For subjects with a partial last dosing date (ie, month and year of last dose are known), the latest of the dispensing dates of study drug bottles, study drug start dates and end dates, and the imputed last dose date [day imputed as 15] will be used as the final imputed last dose date. However if dispensing date's month is after last dose date's month, data query is needed.

If subject died and the death date is complete (ie, not partial date) and before the imputed last dose date, the complete death date should be used as the imputed last dose date.

b) Last Study Date is the latest of the study drug start dates and end dates, the clinic visit dates, and the laboratory visit dates, including the 30-day follow-up visit date, for subjects who prematurely discontinued study or who completed study according to the Study Completion eCRF. If study drug start date or end date is partially missing (ie, only year and month are known), the day will be imputed as 15 for the purpose of this analysis.

If subject died and the death date is complete (ie, not partial date) and before the imputed last study date, the complete death date should be used as the imputed last study date.

#### 12) Duration of baseline ARV regimen

a) Defining ARV Regimen at Baseline:

All subjects are expected to enter the study on DTG + F/TAF or DTG + F/TDF. Using the ARV raw dataset, include all prior and/or current ARVs (ARV.INGRED where ARV.CMSCAT ='Prior ARV" or "Current ARV"), taken on or up to 2 day prior to first dose date (or randomization date if not treated) for randomized phase analysis:

Select only ARV with the start date on or prior to first dose date of randomized study drug, and the end date ongoing or >= the first dosed date of randomized study drug, (For the same ARV, if the stop date of 1 record is on the same date or 1 day before the start date of another record, please combine it as one record)

When determining the baseline ARV regimen, look at the ingredient of drugs, replacing "\_" with "/" (for FTC\_TAF and FTC\_TDF), respectively. Moreover, replace "FTC/" with "F/". Assign an order priority of 1 to "DTG" and 2 to "F/TAF" or "F/TDF" for each subject.

Once the ingredients have been updated and assigned an appropriate priority, transpose the ingredients by subject (using the ingredient as the variable and priority as the id) and concatenate each column with a "+" following the priority specified above. To illustrate this, if a subject is on DTG and FTC\_TAF, then their regimen would be presented as "DTG+F/TAF".

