#### 6.2. Pretreatment Assessments

### **6.2.1.** Screening Visit

Subjects will be screened within 30 days before Day 1 to determine eligibility for participation in the study. The following will be performed and documented at screening:

- Obtain written informed consent(s)
- Obtain medical history including history of HIV-1 disease-related events, and prior medications within 30 days of the screening visit
- If available, obtain documentation of historical genotype(s) (not required for entry to study)
- Complete physical examination (urogenital/anorectal exams will be performed at the discretion of the Investigator)
- 12-lead ECG performed supine
- Height
- Vital signs measurement (blood pressure, pulse, respiration rate, and temperature), including weight
- Obtain blood and urine samples as described in Sections 6.10.1 and 6.10.2
- Review concomitant medications
- Record any SAEs and all AEs related to protocol mandated procedures occurring after signing of the consent form

Subjects meeting all of the inclusion criteria, and none of the exclusion criteria, will return to the clinic within 30 days after screening for the Day 1 Visit into the study. Subjects must continue to take their prior treatment regimen up until their scheduled Day 1 visit.

From the time of obtaining informed consent through the first administration of study drug, record all SAEs, as well as any AEs related to protocol-mandated procedures on the adverse events eCRF. All other untoward medical occurrences observed during the screening period, including exacerbation or changes in medical history are to be captured on the medical history eCRF. See Section 7 Adverse Events and Toxicity Management for additional details.

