# 4. SUBJECT DISPOSITION

## 4.1. Subject Enrollment and Disposition

## 4.1.1. Subject Enrollment

The number and percentage of subjects randomized at each region, country, and investigator will be summarized by treatment group and overall using the safety analysis set. The region definition is provided in Appendix 2. The denominator for this calculation will be the number of subjects in the safety analysis set. Similarly, the number and percentage of subjects enrolled in each randomization stratum will be summarized based on reclassified strata using baseline NRTI backbone based on the Non-Study ARV Medication eCRF, and baseline NRTI resistance data as determined by Gilead Virology based on virology data instead of using interactive web response system (IWRS) data.

If there are discrepancies between IWRS and collected data with regard to stratum assignment, a listing of the discrepancies will be provided.

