## 7.2.5. Renal-Related Laboratory Evaluations

## 7.2.5.1. Serum Creatinine and eGFR $_{CG}$

Baseline, postbaseline, and change from baseline in serum creatinine and eGFRCG will be summarized by treatment group and visit using descriptive statistics based on the Safety Analysis Set for randomized phase analysis and All B/F/TAF Analysis Set for all B/F/TAF analysis, respectively. Baseline and change from baseline will be compared between the 2 treatment groups using a 2-sided Wilcoxon rank sum test for randomized phase analysis. No formal statistical testing is planned for all B/F/TAF analysis.

Median (Q1, Q3) of change from baseline in serum creatinine and eGFRCG over time will be plotted by treatment group based on the Safety Analysis Set for randomized phase analysis and All B/F/TAF Analysis Set for all B/F/TAF analysis, respectively.

Summary of baseline, postbaseline, and change from baseline in serum creatinine and  $eGFR_{CG}$  will be repeated within each subgroup of baseline NRTI backbone based on the Non-Study ARV Medication eCRF (F/TAF vs. F/TDF) based on the Safety Analysis Set for randomized phase analysis. P-values comparing the difference between the 2 treatment groups in baseline values and the change from baseline in metabolic assessment will be generated from a 2-sided Wilcoxon rank sum test for randomized phase analysis.

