## b) Calculation of the duration of baseline ARV regimen

Duration of baseline regimen DTG + FTC/TAF or DTG + FTC/TDF prior to the randomized phase 1st dose date (or B/F/TAF first dose date) is defined as (End Date – Start Date+1) (ie, equal to [randomized first dose date (or B/F/TAF first dose date)-1 – start date of prior ARV +1)]. Duration will be expressed in years so that duration in days will be divided by 365.25 days.

**End date** is defined as randomized phase first dose date (or B/F/TAF first dose date) -1 or randomized date if randomized but not dosed,

Start Date: The use of baseline ARV regimen: DTG + DESCOVY (FTC/TAF) or DTG + TRUVADA

Step 1: Use the following rules to handle any incomplete start dates

- If only month and year are available, day will be first imputed as 15th, then imputed as minimum of (the start date of the ARV, randomized phase 1st dose date-1, the stop date of the same ARV)
- If only year is available, month and day will be first imputed July 1st of the year, then imputed as minimum of (the start date of the ARV, randomized phase 1st dose date-1, the stop date of the same ARV)
- No imputation applied for date missing completely

(Use the following rules to handle any incomplete stop dates, if needed

- If only month and year are available, day will be first imputed as 15th, then imputed as minimum of (the randomized phase 1st dose date-1, the stop date of the same ARV)
- If only year is available, month and day will be first imputed July 1st of the year, then imputed as minimum of (randomized phase 1st dose date-1, the stop date of the same ARV)
- No imputation applied for date missing completely)

Step 2: Select ARVs with start date on or prior to the randomized phase 1st dose date (or B/F/TAF first dose date for all B/F/TAF analysis)

Step 3: For each subject, find the first dose date and last dose date for each study drug component:

For the same ARV, if the stop date of 1 record is on the same date or 1 day before the start date of another record, please combine it as one record.

 Select all ARVs containing the wording of 'DTG' in ARV.INGRED and select the latest start date (D1\_DTG)

- Select all ARVs containing the wording of 'FTC\_TAF' in ARV.INGRED and select the latest start date (D1\_DESCOVY)
- Select all ARVs containing the wording of 'FTC\_TDF' in ARV.INGRED and select the latest start date (D1\_TRUVADA)

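### SAP Appendix 8 item 12a gives two conflicting date rules for the baseline antiretroviral regimen; coded literally, the stricter one rejects a prior drug stopped one or two days before Day 1

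*SAP*

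**What the plan says.** Item 12 of SAP Appendix 8 deals with the duration of the baseline antiretroviral regimen. Part (a) defines the regimen and part (b) computes its duration.

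Part (a) has two date conditions in sequence. The opening sentence takes in prior and current antiretrovirals "taken on or up to 2 day prior to first dose date (or randomization date if not treated) for randomized phase analysis". The selection step that follows keeps only records that started on or before the first randomised dose and have "the end date ongoing or >= the first dosed date of randomized study drug". The retained ingredients are then joined into a label such as DTG+F/TAF.

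Part (b) needs an end date for the duration formula. That date "is defined as randomized phase first dose date (or B/F/TAF first dose date) -1", with the randomisation date used for subjects who were never dosed.

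On the clinical side, Protocol 6.2.1 states: "Subjects must continue to take their prior treatment regimen up until their scheduled Day 1 visit". Protocol 6.2.2 has the first study dose given under observation at that visit.

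The SAP uses the prior backbone in four places. SAP 4.1.1 summarises enrolment by "reclassified strata using baseline NRTI backbone based on the Non-Study ARV Medication eCRF", in preference to IWRS data. SAP 5.2 puts the backbone in the baseline table. SAP 7.2.3 repeats the fasting metabolic summaries by backbone. In SAP 7.2.5.1 the creatinine and eGFR summary "will be repeated within each subgroup of baseline NRTI backbone based on the Non-Study ARV Medication eCRF (F/TAF vs. F/TDF").

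**The concern.** The two conditions in item 12a give different answers for the same record. A subject who takes the last prior dose the day before the Day 1 visit has complied with the protocol. The opening sentence keeps that subject's prior drugs; the selection step discards them. The selection step is the restrictive, directly programmable one, so literal coding would leave the regimen blank.

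The selector is also an odd definition of a prior regimen. Under SAP 7.4.2, a medication is concomitant if it starts no later than last dose and stops no earlier than first dose, and Appendix 8 item 18 applies similar logic to non-study antiretrovirals. Any record that passes the item 12a selector therefore also counts as overlapping study drug. A clean switch, with no overlap, is what it rejects.

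If the same derivation feeds the backbone variable, membership of the F/TAF and F/TDF groups in the renal and metabolic subgroup summaries would depend partly on how a site recorded a stop date. Two programmers could also build different subgroups from the same specification.

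**Working it through.** The plan gives no figure to reproduce here, so the check is on the logic of the date rules.

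**Inputs.** Let d = recorded stop date of the prior drug minus first study dose date, in days, taking the stop date as the last day the drug was taken.

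- Opening sentence of item 12a: keep if ongoing or d ≥ −2.
- Selection step of item 12a: keep if ongoing or d ≥ 0.
- End-date convention in item 12b: d = −1.
- Safety analysis set and FAS: N = 565 (SAP Appendix 3).

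**Step 1: apply the rules.**

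| Stop relative to first dose | Opening sentence | Selection step | Both applied |
|---|---|---|---|
| −3 | out | out | out |
| −2 | in | out | out |
| −1 | in | out | out |
| 0 | in | in | in |
| +1 | in | in | in |
| ongoing | in | in | in |

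The rules disagree at exactly two values, −2 and −1. Applying both in sequence gives the selector's answer everywhere, so the two-day lookback has no effect.

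**Step 2: compare with item 12b.** Its end date has d = −1, and −1 ≥ 0 is false. A record stopped on the date that item 12b uses to close the regimen would not be selected by item 12a.

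**Step 3: trace the reach.** SAP 4.1.1, 5.2, 7.2.3 and 7.2.5.1 all base the backbone on the Non-Study ARV Medication eCRF. None of them cites Appendix 8 item 12. Item 12a is, however, the only place where the SAP sets out how to turn those records into a regimen. If it is the source, a blank regimen means no backbone value. Appendix 8 item 9 leaves missing categories out of percentages and categorical p-values, and a subject with no backbone value belongs to neither subgroup. No fallback is given.

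**Step 4: what is not reached.** Randomisation used the IWRS stratum. The primary analysis (SAP 6.1.1.4) and the analysis of HIV-1 RNA below 50 copies/mL (SAP 6.1.2.2.1) use exact intervals without backbone strata. The efficacy subgroups in SAP 3.4.1 do not include backbone. The CD4 model in SAP 6.1.2.2.3 has treatment as its only term, although Protocol 8.5.2 lists prior NRTI use as a factor. The overall renal and metabolic summaries do not use backbone. Step 2 of item 12b selects on start date alone, so the duration calculation need not lose anyone.

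**Step 5: size.** The documents give no distribution of prior-drug stop dates. The number affected is between 0 and 565.

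**Step 6: test the correction.** With the selector changed to d ≥ −2, the records at −2 and −1 come back in, −3 stays out, and the two sentences agree at every value in the table.

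**The case against.** The strongest reply is that this is a wording inconsistency in a programming appendix. The opening sentence plainly intends to keep subjects who stopped just before Day 1, and a sensible programmer would follow it. Sites may also have recorded the Day 1 switch date itself as the stop date, which passes both rules; the documents contain no eCRF instruction for that field. Item 12a says all subjects are expected to enter on one of the two regimens, and SAP 4.1.1 calls for a listing of discrepancies between IWRS and collected strata, so many blanks would be noticed. All of this stands as a limit on the likely damage. It does not settle which sentence governs, and a listing shows a problem without saying how to resolve it.

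Three stronger readings are tempting, and the documents do not support them.

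- A reader might infer that everyone who stopped the day before Day 1 loses the stratum and drops out. That takes one of two conflicting sentences as decisive and treats the link from item 12a to the stratum as stated. It is an inference.
- A reader might infer that every partial stop date must fail, because item 12b sets a provisional date, "then imputed as minimum of (the randomized phase 1st dose date-1, the stop date of the same ARV"). That imputation is parenthetical, applies only if needed, and belongs to the duration calculation. Nothing says that imputed stop dates feed the item 12a selector.
- A reader might take item 12b's end date as proof that recorded stop dates fall on the day before first dose. It is a convention for the duration formula. It shows that the two parts do not fit together, and says nothing about what sites entered.

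**Conclusion.** The contradiction within item 12a is real and can be read directly from the text. As coded literally, the selector rejects prior drugs stopped one or two days before first dose, although such dates are compatible with the protocol and fall inside the item's own lookback.

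The consequence is conditional. It requires that the program follows the selector, that item 12a supplies the backbone, and that some subjects have a recorded stop date at −2 or −1. If all three hold, those subjects would be missing from the stratum and baseline tables and from the renal and fasting-metabolic summaries by backbone. The count cannot be estimated from the documents and may be zero. No primary or secondary efficacy analysis in the SAP depends on it. This should be corrected in the specification, but it does not threaten the trial's main conclusion.

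**What to change.** Make three changes to the SAP.

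1. In Appendix 8 item 12a, change the end-date condition so that a record qualifies if it is ongoing or if its end date is on or after the first dose date of randomised study drug minus 2 days.
2. State in item 12a that this derivation supplies the F/TAF versus F/TDF backbone, and refer to it from SAP 4.1.1, 5.2, 7.2.3 and 7.2.5.1.
3. Use the IWRS backbone stratum only where the derived regimen is still blank. Record this as an exception in SAP 4.1.1, which otherwise prefers collected data to IWRS.

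Do not go further and move partial stop dates to the day before first dose. A subject who changed from F/TDF to F/TAF earlier in the year of first dose, with only a year recorded for the F/TDF stop, would then appear to be on both at baseline. Item 12a gives both the same priority, so they would collide.

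The cost is a few lines of specification and a check of the existing program. No new data are needed. SAP 2.2.1 says the Week 48 analysis has been done, so confirm which rule was coded then and report any change in subgroup membership.

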## b) Calculation of the duration of baseline ARV regimen

Duration of baseline regimen DTG + FTC/TAF or DTG + FTC/TDF prior to the randomized phase 1st dose date (or B/F/TAF first dose date) is defined as (End Date – Start Date+1) (ie, equal to [randomized first dose date (or B/F/TAF first dose date)-1 – start date of prior ARV +1)]. Duration will be expressed in years so that duration in days will be divided by 365.25 days.

**End date** is defined as randomized phase first dose date (or B/F/TAF first dose date) -1 or randomized date if randomized but not dosed,

Start Date: The use of baseline ARV regimen: DTG + DESCOVY (FTC/TAF) or DTG + TRUVADA

Step 1: Use the following rules to handle any incomplete start dates

- If only month and year are available, day will be first imputed as 15th, then imputed as minimum of (the start date of the ARV, randomized phase 1st dose date-1, the stop date of the same ARV)
- If only year is available, month and day will be first imputed July 1st of the year, then imputed as minimum of (the start date of the ARV, randomized phase 1st dose date-1, the stop date of the same ARV)
- No imputation applied for date missing completely

(Use the following rules to handle any incomplete stop dates, if needed

- If only month and year are available, day will be first imputed as 15th, then imputed as minimum of (the randomized phase 1st dose date-1, the stop date of the same ARV)
- If only year is available, month and day will be first imputed July 1st of the year, then imputed as minimum of (randomized phase 1st dose date-1, the stop date of the same ARV)
- No imputation applied for date missing completely)

Step 2: Select ARVs with start date on or prior to the randomized phase 1st dose date (or B/F/TAF first dose date for all B/F/TAF analysis)

Step 3: For each subject, find the first dose date and last dose date for each study drug component:

For the same ARV, if the stop date of 1 record is on the same date or 1 day before the start date of another record, please combine it as one record.

 Select all ARVs containing the wording of 'DTG' in ARV.INGRED and select the latest start date (D1\_DTG)

- Select all ARVs containing the wording of 'FTC\_TAF' in ARV.INGRED and select the latest start date (D1\_DESCOVY)
- Select all ARVs containing the wording of 'FTC\_TDF' in ARV.INGRED and select the latest start date (D1\_TRUVADA)

